6.7 Laboratory Monitoring

[figure not shown]
Blood and serum (one tube) will be collected twice for research biomarker, correlative studies. The first will be collected at baseline, prior to initiation of NFV, and the second after completion

of lead-in NFV. All subjects on study will be monitored with complete blood counts with differential and comprehensive metabolic panel at the discretion of the treating physicians. All other laboratory tests will be performed as clinically indicated.

6.8 Study Visit Schedule

- 6.8.1** After the subject consents and is deemed eligible for the study, the study drug (NFV) will be dispensed and a baseline blood/serum draw (one tube) for research laboratory studies will be taken. Subjects will then be seen weekly during radiotherapy in the outpatient clinics to assess treatment-related toxicities. The following will be performed: (1) history and targeted physical examination and (2) laboratory evaluations as considered appropriate by study physicians.
- 6.8.2** FDG PET-CT scan will be performed at three months after the completion of radiotherapy as standard of care, in order to assess response to treatment, and for restaging purposes.
- 6.8.3** After discontinuation of nelfinavir therapy, follow-up including laboratory tests and radiographic studies will be scheduled as per standard of care. Toxicities will be evaluated up to the first standard of care follow-up visit after completion radiation, after which we will then follow for survival.

6.9 Study Visit Flowchart

7 Statistical Plan

A 28 patient phase II trial of NFV and concurrent chemo/RT with measurements of hypoxia by $^{18}\text{EF-5}$ or FMISO PET imaging and serum biomarkers will be performed. Locoregional control is the primary endpoint, defined from first day of chemo/RT+NFV to local or regional progression. Distant progression and patients free of locoregional control will be censored. The "pre and post-NFV" measurements mentioned below, refer to samples obtained before and after a 7-14 day run-in period of NFV prior to chemo/RT. These pre/post-NFV changes are evaluated as "early change" predictors of treatment outcome. Hypotheses tested by statistical analyses are:

NFV given with chemo/RT will improve locoregional control (primary objective) will be tested by comparing our locoregional control to a historical result by log rank test with adequate power as described below. In a randomized pilot study by Rischin (JCO 24:2098-2104, 2006) in head and neck cancer, patients with hypoxic tumors who received concurrent chemoradiotherapy had a 3-year locoregional control rate of 30%, while patients who received the hypoxia-activating pro-drug tirapazamine and concurrent chemoradiotherapy had a 3-year locoregional rate of 95%. Although the difference in local control was stunning, the sample sizes of these groups was very modest. Therefore, we have powered our study conservatively, in order to detect a more modest treatment effect.

Starting with this amendment, a total of 28 patients will be enrolled over 4 years, assuming a rate of 7 patients per year. To date, only 2 larynx cancer patient had been enrolled on this trial, so 4 years of accrual will be needed to meet the target sample size. We will then follow patients for an additional 6 months. There will be 85% power to detect a 30% absolute increase in 3-year locoregional control from a 40% rate for standard concurrent chemoradiotherapy to 70% for Nelfinavir and concurrent chemoradiotherapy, using a 1-sided log rank test at a 5% type I error rate. Power calculated with SWOG software (http://www.swogstat.org/stat/public/one_nonparametric_survival.htm).

NFV will reduce tumor hypoxia will be tested by comparing pre and post-NFV hypoxia (i.e., $^{18}\text{EF-5}$ uptake expressed as a tumor to muscle (TMR) ratio) by Student's paired t-test. Transformation of the ratio may be necessary in order to meet the normality assumption of the t-test. Assuming an effect size (δ), in units of Std Dev of differences ($\delta = |\mu_d|/\sigma_d$), of $1/2\sigma_d$, with 28 patients enrolled there is 82% power to detect the difference between pre/post-NFV values using a 1-sided paired t-test at a stricter 5% type I error, used to control false positive conclusions in our correlative analyses.

Baseline hypoxia, and glucose uptake are predictive of treatment outcome will be tested by an exploratory analysis using Cox regression. Each variable will be tested in a univariate survival model to assess association with locoregional control. The hazard ratio, 95% confidence interval and statistical significance will be determined for each variable. Exploratory analyses will also evaluate differences between Nelfinavir responders and nonresponders. The definition of "NFV responder" requires greater knowledge about the distribution and variance of the baseline TMR. For example, a decrease in TMR to <1.25 or percent decrease from baseline of $>50\%$ may be reasonable definitions. This exploratory analysis yields estimates of treatment outcomes within response groups.

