4.6 Off-Study Criteria

- Extraordinary Medical Circumstances. If at any time the constraints of this protocol are detrimental to the subject's health, the subject will be removed from protocol therapy. In this event, the reasons for withdrawal will be documented.
- Subject's refusal to continue treatment. In this event, the reasons for withdrawal will be documented.
- Any patient who experiences any Grade III or higher toxicity related to ¹⁸F-FMISO and not related to the underlying disease.
- Patients will be considered "off-study" at the completion of study procedures. This will occur at the completion of 3 month follow up PET/CT.
- Patients may be taken off study at any time at the discretion of the Principal Investigator
- Every effort will be made to follow subjects off study for toxicity and survival.

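### The only censoring rule for the primary endpoint censors patients without locoregional control, who are the patients with the event; the wording needs correcting

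*Combined protocol and SAP*

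**What the plan says.** Section 7 of the combined protocol and SAP sets out the endpoint and its censoring in two adjacent sentences. The first reads "Locoregional control is the primary endpoint, defined from first day of chemo/RT+NFV to local or regional progression". The second reads "Distant progression and patients free of locoregional control will be censored".

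Later in section 7 the design target is an "increase in 3-year locoregional control from a 40% rate for standard concurrent chemoradiotherapy to 70% for Nelfinavir" given with the same treatment. It is tested one-sided at 5% with 28 patients, 4 years of accrual and 6 further months of follow-up, for a stated power of 85%.

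The exploratory part of section 7 uses the endpoint again: "Each variable will be tested in a univariate survival model to assess association with locoregional control". It restates neither an event nor a censoring rule. Sections 2.1 and 3.2 name locoregional control as the primary objective and endpoint, also without a censoring rule.

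**The concern.** The two sentences cannot both be followed. A patient free of, that is without, locoregional control has failed locally or regionally. The first sentence counts that patient as an event and the second censors the same patient. The censoring sentence also does not mention the patients it should have named, those who remain controlled.

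This matters because the sentence decides who counts as a failure in the primary comparison with the historical rate, and it is the only rule available for the Cox models on the same endpoint. In a single-arm trial no concurrent control group is analysed under the same rule, so the definition of failure bears directly on the result. The written plan should not need silent correction by whoever runs the analysis.

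**Working it through.** **1. The sentences side by side.**
- Event: the time is "defined from first day of chemo/RT+NFV to local or regional progression". Progression is the failure.
- Censored: patients with distant progression, and patients without locoregional control.
- Direction of the word 'control': in the power statement it rises from 40% to 70% with benefit, so control is the good outcome and its absence is failure.

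The second censored group is therefore the event group. Putting 'progression' in place of 'control' removes the conflict and leaves both sentences consistent with the power statement. The first censored group, distant progression, does not conflict with the event definition.

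**2. The plan's own power figure.** Inputs from section 7: N = 28, accrual 4 years, added follow-up 0.5 year, 3-year control 40% (null) and 70% (alternative), one-sided 5%. Assumptions: constant hazard, uniform accrual, administrative censoring only, and a Kaplan-Meier test at 3 years.
- Hazards: λ0 = −ln(0.40)/3 = 0.3054; λ1 = −ln(0.70)/3 = 0.1189 per year.
- Probability of still being under follow-up at time t: G(t) = 1 for t ≤ 0.5, and (4.5 − t)/4 after that.
- Variance of the cumulative hazard at 3 years: (1/28) × ∫ from 0 to 3 of λ / [exp(−λt) G(t)] dt = 0.0854 (null) and 0.0233 (alternative).
- Standard errors of 3-year control: 0.40 × √0.0854 = 0.117; 0.70 × √0.0233 = 0.107.
- Rejection limit: 0.40 + 1.645 × 0.117 = 0.592.
- Power: Φ[(0.70 − 0.592)/0.107] = Φ(1.01) = 84%. On the log(−log) scale it is 83.6%. Stated: 85%.

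One-sample log-rank approximations under the same assumptions give 82.8% (null variance) and 93.5% (null and alternative variances). The stated figure is approximately reproduced. The censoring sentence is not an input to any of these formulas. The match shows that the design was built with control as the good outcome; it does not test the sentence.

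**3. How many patients the wording concerns.** Expected events = 28 × ∫ from 0 to 4.5 of λ exp(−λt) G(t) dt.
- At 40% control: 14.1 with progression, 28 − 14.1 = 13.9 without.
- At 70% control: 7.0 with progression, 28 − 7.0 = 21.0 without.

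The sentence as written names the 7 to 14 who progress and omits the 14 to 21 who do not.

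**4. What censoring at distant progression does to these figures.** The documents give no rate, so this range is an assumption. Let independent extra censoring remove a proportion q by 3 years, at a constant rate −ln(1 − q)/3, and multiply G(t) by the corresponding exponential.

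| q by 3 years | Power, 3-year Kaplan-Meier test | Expected events at 70% control |
|---|---|---|
| 0 | 84% | 7.0 |
| 20% | 79% | 6.3 |
| 40% | 72% | 5.6 |

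The agreement with 85% therefore holds only when administrative censoring is the sole source. This follows from the part of the rule that is not in dispute, and correcting the slip does not alter it.

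**The case against.** The best defence is that the document resolves the meaning itself. The preceding sentence fixes the event, control is plainly the favourable direction, and the disputed group is listed beside distant progression, which is a non-event. For a time-to-event endpoint analysed by log-rank and Cox methods, censoring patients who have not had the event is the default whether or not it is written. All of this stands. It limits the severity, but it does not make the sentence correct, and nothing elsewhere in the document overrides it.

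A reader might go further and infer that the trial would declare benefit whatever the true control rate, since censoring every failure leaves no events. The documents do not support that. It requires discarding the event definition in the adjacent sentence, and with zero events the test statistic is favourable by construction. It describes an analysis nobody would run and is no measure of the size of this problem.

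A reader might also treat the missing censoring date and the silence on death without locoregional progression as part of the same error. Patients go off study after the 3-month scan (section 4.6: "This will occur at the completion of 3 month follow up PET/CT"). Section 6.8 then says "follow-up including laboratory tests and radiographic studies will be scheduled as per standard of care" and, once toxicity assessment ends, "after which we will then follow for survival". The last locoregional assessment and the last contact can therefore differ. These are reasonable things to clarify, but they are separate choices that the contradiction does not force.

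**Conclusion.** The censoring rule is wrong as written, at moderate severity. It contradicts the event definition in the sentence before it, it is the only censoring rule for the primary endpoint, and the Cox models on locoregional control have no other. It is almost certainly a drafting slip, and a false trial result is not the realistic risk.

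The wording concerns about 7 (at 70% control) to 14 (at 40%) of 28 patients, assuming constant hazards, uniform accrual and administrative censoring only. A reader might conclude that the sample size or the 85% power is also in error. The check does not show that: about 84% is obtained on the ordinary reading. That agreement does depend on there being no other censoring, and the plan's own censoring at distant progression would reduce power by an amount the documents do not allow to be fixed.

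**What to change.** Replace the censoring sentence in section 7 with: 'Local or regional progression is the event; patients with distant progression and patients free of locoregional progression will be censored.' State that the same rule applies to the exploratory Cox models on locoregional control.

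The cost is one sentence. Sample size, test and follow-up do not change. It would help to note beside the power statement that the figure allows for administrative censoring only, if that is how it was obtained.

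Optionally, the same edit could state the censoring date (last locoregional assessment or last contact) and how death without locoregional progression is handled. Correcting the error does not depend on either.

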Diagnosis and Main Inclusion Criteria	Stage III, IVa, or IVb squamous cell carcinoma of the oral cavity, oropharynx, larynx, or hypopharynx with ECOG performance status 0-2
Study Product, Dose, Route, Regimen	
Nelfinavir (Viracept®) 1250 mg By mouth two times a day Medicine should be taken with food, preferably high in fat.
 
¹⁸F-FMISO 5-10 mCi Intravenous bolus injection

Duration of administration	Treatment to start 7-14 days prior to radiation and continued throughout radiation and standard chemotherapy.
Reference therapy	Combination of standard chemotherapy and radiation therapy
Statistical Methodology	This is a single arm, phase II study of nelfinavir (1250 mg given po bid) and concurrent chemoradiotherapy in locally advanced head and neck cancer. Locoregional control will be compared to published historical results. There will be a total of 28 patients enrolled on the study.

1 Introduction

This is a Phase II trial of definitive chemoradiotherapy (CTRT) given with the protease inhibitor, Nelfinavir (NFV), in patients with locally advanced head and neck cancer. Eligible patients will receive a “lead-in” period of Nelfinavir (1250 mg po bid) for 7-14 days prior to initiation of CTRT. Nelfinavir will then be given concurrently with platinum-based chemotherapy and radiation therapy (planned total dose of 70 Gy over 7 weeks).

All patients will also undergo the following:

- 1) ^{18}F -FMISO PET/CT: this scan assesses tumor hypoxia. Patients will undergo 2 separate ^{18}F -FMISO PET/CT scans: the first at baseline to determine baseline tumor hypoxia, the second after a 7-14 day lead-in of NFV prior to CTRT (to determine change in tumor oxygenation secondary to NFV). Six patients will receive 3 separate ^{18}F -FMISO PET/CT, the first at baseline to determine baseline tumor hypoxia, the second also at baseline to determine reliability of the scan for test-retest purposes, the third after a 7-14-day lead-in of NFV.
- 2) ^{18}F -FDG PET/CT: this scan assesses glucose uptake. Patient will undergo 2 separate ^{18}F -FDG PET/CT scans: the first at baseline as part of routine clinical care, for purposes of radiation treatment planning and the second after a 7-14 day lead-in of NFV prior to CTRT (to determine change in tumor glucose uptake secondary to NFV).

The primary objective of the study will be to determine whether NFV, given with definitive CTRT, will improve locoregional control in locally advanced head and neck cancer.

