3.3 Secondary Study Endpoints

¹⁸F-FMISO PET/CT

Patients will receive two hypoxia PET/CT scans with either ¹⁸F-FMISO or ¹⁸F-EF5 (initial 15 subjects were completed using EF-5, subsequent subjects will be imaged with FMISO): the first at baseline to determine baseline tumor hypoxia, and the second after a 7-14 day lead-in of NFV prior to CTRT (to determine change in tumor oxygenation secondary to NFV). Tumor regions of interest (ROIs), corresponding to the primary tumor site and pathologic lymph nodes will be drawn with the help of CT images. Tumor to muscle ratios (TMR) will be determined for each ROI. A TMR of ≥ 1.3 will be considered significant for hypoxia, and a reasonable starting point in which the outcome of the addition of NFV to CTRT can be evaluated. The ability of NFV to reduce tumor hypoxia will be tested by comparing pre and post-NFV hypoxia (i.e., ¹⁸F-FMISO uptake expressed as a TMR) by Student's paired t-test.

¹⁸F-FDG PET/CT

Patients will undergo 2 separate ¹⁸F-FDG PET/CT scans: the first at baseline as part of routine clinical care, for purposes of radiation treatment planning and the second after a 7-14 day lead-in of NFV prior to CTRT (to determine change in tumor glucose uptake secondary to NFV). That

change in hypoxia will correlate with change in glucose uptake will be tested by Pearson's correlation.

That baseline hypoxia and glucose metabolism are predictive of treatment outcome will be tested by Cox regression analysis.

NCI Common toxicity grades will be employed.

4 Subject Selection and Withdrawal

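### The exploratory Cox analysis of baseline TMR has no tracer term, although EF5 and FMISO values are split entirely by enrolment order

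*Combined protocol and SAP*

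**What the plan says.** Section 3.3 gives the tracer rule: "initial 15 subjects were completed using EF-5, subsequent subjects will be imaged with FMISO". Sections 1.1 and 3.2 say the same of the first 15 subjects. The opening of Section 7 describes a single trial with either tracer: "A 28 patient phase II trial of NFV and concurrent chemo/RT with measurements of hypoxia by" EF-5 or FMISO.

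Three uses of TMR compare patients with one another:

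- **Baseline TMR and outcome.** Section 7 says that this "will be tested by an exploratory analysis using Cox regression", and then: "Each variable will be tested in a univariate survival model to assess association with locoregional control". A hazard ratio, 95% confidence interval and significance are to be reported for each variable. Section 7 also treats pre/post changes as early predictors of outcome.
- **TMR change and FDG change.** Section 3.3: "change in hypoxia will correlate with change in glucose uptake will be tested by" Pearson's correlation.
- **Thresholds.** Section 3.3: "A TMR of ≥ 1.3 will be considered significant for hypoxia", described there as a starting point. Sections 3.2 and 7 offer a TMR below 1.25 or a fall of more than 50% as examples of a responder rule and leave the definition open.

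No section gives a tracer term, stratification, tracer-specific thresholds, a cross-calibration or a sensitivity analysis by tracer. The six-patient test-retest scans in Section 1 compare FMISO with FMISO, so they cannot link the two scales.

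**The concern.** In the paired pre/post comparison each patient should be imaged with the same tracer twice, so tracer is held constant within the pair. A Cox model on baseline TMR compares patients with each other, and there tracer does not drop out. Every EF5 patient was enrolled before every FMISO patient, so a difference in TMR scale also coincides with any drift in case mix or treatment. Sections 6.3 and 6.4 allow several systemic regimens and either photon or proton radiotherapy, so drift over about four years of accrual is possible, though not shown.

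Two harms follow. A scale difference alone adds variation unrelated to hypoxia and dilutes a real association. A scale difference together with an era difference in outcome lets tracer act as a confounder, which can create an association or hide one. Section 1.1 makes reduced hypoxia the central hypothesis for how nelfinavir works, so these results will colour how the trial is read even though Section 7 labels them exploratory.

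**Working it through.** **1. The plan's only power figure for hypoxia.** This is the paired t-test in Section 7: effect 0.5 SD of the differences, one-sided 5%, 28 patients, stated power 82%. Exact noncentral t with df = 27 and noncentrality 0.5 × √28 = 2.65 gives 82.5%, so it reproduces. With 15 patients alone it is 57.8% and with 13 alone 52.2%. The figure therefore counts all 28 patients together. This is only modest evidence of pooling, because that paragraph names EF-5 alone and may not have been updated after the switch. The Cox and Pearson analyses have no stated power.

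**2. Dilution from an offset.** Let the tracers differ by c within-tracer SDs, with a share p = 15/28 on EF5. Then p(1 − p) = 15 × 13 / 28² = 0.249. The share of pooled TMR variance due to tracer is 0.249c² / (1 + 0.249c²), and a correlation shrinks by √(1 − share).

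| c (assumed) | Share due to tracer | Shrinkage factor |
|---|---|---|
| 0.5 | 6% | 0.97 |
| 1 | 20% | 0.90 |
| 1.5 | 36% | 0.80 |
| 2 | 50% | 0.71 |

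The count of 13 assumes that the 15 EF5 subjects belong to the 28. The Study Summary says "There will be a total of 28 patients enrolled on the study", but Section 7 says "Starting with this amendment, a total of 28 patients will be enrolled over 4 years, assuming a rate of 7 patients per year". If 28 FMISO patients followed the 15, p(1 − p) = 15 × 28 / 43² = 0.227, and the factors at c = 1 and 2 are 0.90 and 0.72. The conclusion does not depend on the reading.

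**3. Cox model by simulation.** Inputs are 15 + 13 patients, accrual over 4 years and analysis 6 months later (Section 7). Assumed are 3-year control of 55%, midway between the plan's 40% and 70%, so the baseline hazard is −ln(0.55)/3 = 0.199 per year; observed TMR = true hypoxia + c × tracer; and a two-sided 5% test.

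| Offset c | Era HR | False positives, pooled / stratified | Power at HR 2 per SD, pooled / stratified |
|---|---|---|---|
| 0 | 1 | 5.0% / 4.8% | 56% / 54% |
| 1 | 1 | 4.9% / 5.3% | 48% / 54% |
| 2 | 1 | 5.8% / 5.8% | 34% / 55% |
| 0 | 3 | 5.6% / 5.0% | 62% / 64% |
| 1 | 2 | 8.2% / 6.1% | 72% / 61% |
| 1 | 3 | 12.3% / 5.9% | 83% / 65% |
| 2 | 2 | 12.4% / 5.2% | 67% / 62% |
| 2 | 3 | 23.3% / 4.9% | 85% / 65% |

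False positives need both an offset and an era effect; neither alone is enough. Here both act in the same direction, so the higher pooled power in the last four rows is bias rather than gain. Under a different assumed follow-up (uniform 0.5 to 4.5 years, about 10 to 15 events), pooled power is 45 to 28% against about 50%, and false positives are 6 to 22% against 4 to 5%. Taken together, the ranges are about 48 to 28% for pooled power and 6 to 23% for false positives.

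**4. TMR change and FDG change.** A constant additive offset cancels: (post + c) − (pre + c) = post − pre. What remains is a difference in scale. With a true correlation of 0.5, a 1.5- to 2-fold scale difference gives pooled power of 78 to 75%, against about 78% with scaling within tracer. A larger effect needs mean TMR change to differ by tracer and FDG change to differ by era. With a 1 SD difference in each and no true correlation, the pooled false-positive rate is 18% against 5% adjusted. That 1 SD is twice the 0.5 SD nelfinavir effect the plan assumes.

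**The case against.** The strongest reply is that pooling is never stated. Section 3.3 names only FMISO for the t-test and Section 7 names only EF-5, and the Cox sentence does not mention tracer. That is correct: pooling is an inference from the univariate wording and the 28-patient power figure. But an analyst who follows the wording would fit one model without a tracer term.

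A reader might also infer that the plan applies one hypoxia cut-off to every patient. The documents do not support this. The 1.3 value is a starting point that no Section 7 test uses, and the 1.25 and 50% rules are examples. A percentage fall would also remove a purely multiplicative tracer difference. What stands is that any rule fixed later should not be set on a mixed distribution.

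A reader might infer as well that the correlation with FDG is badly weakened. It is not, because an additive offset cancels in the change and plausible scale differences cost only a few points.

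Finally, the highest Cox figures combine the top of both assumed ranges, which the documents support neither singly nor together. The lowest false-positive figure, 6%, is close to simulation error: at 1,200 runs the standard error is √(0.05 × 0.95 / 1200) = 0.6 points. The analysis is weak under either method. All of this limits the size claimed, but it does not supply the missing tracer term.

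**Conclusion.** The point holds for the exploratory Cox analysis of baseline TMR, and for TMR change where it is used as an early predictor of outcome. Tracer and era cannot be separated, the specified model has no term for either, and agreement of the two scales is not shown. The size cannot be known from the documents. The ranges in step 3 of the working rest on an offset of 1 to 2 SD and, for false positives, an era hazard ratio of 2 to 3. With no offset there is no distortion.

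For the FDG correlation the gain from adjustment is small, unless the tracers differ strongly in scale or FDG change also shifted by era. The primary endpoint does not use TMR, and the paired test compares each patient with himself or herself, so neither is affected. This is a cheap improvement to secondary and exploratory analyses that should be made before they are run.

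**What to change.** In Section 7:

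- Stratify the Cox models for baseline TMR, and for TMR change as an early predictor, by tracer. Standardise log TMR (or its change) within tracer, and show results by tracer beside the combined estimate. Stratification removes a constant shift between tracers, and standardisation removes a difference in spread.
- Define any TMR threshold or responder rule within tracer once the distributions are known, or use TMR change as a continuous variable.
- For the FDG correlation, standardise TMR change within tracer and report a partial correlation adjusted for tracer. Adjustment without rescaling does not help with a scale difference: at a 2-fold difference, power is 73% adjusted against 74% pooled.
- State that the 15 EF5 subjects do or do not count toward the 28.

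The cost is wording, since tracer is known for every subject. If the tracers are interchangeable, Cox power falls by up to about 4 points (56 to 54% in the table; 52 to 48% under the other follow-up assumption) and correlation power by up to about 3 (80 to 77%). With 10 to 15 events each stratum holds roughly 5 to 8; the stratified powers above already reflect this. Standardising within tracer also sets aside any true difference in hypoxia between eras, but these data cannot separate that from tracer in any case.

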3.2 Primary Study Endpoints

The intent of this protocol is to determine the efficacy of NFV + CTRT for locally advanced, HPV-negative head and neck cancer. Therefore, the primary endpoint will be locoregional control. However, secondary objectives will be (1) to determine the effect of NFV on hypoxia as assessed by ¹⁸F-FMISO PET/CT imaging (the initial 15 subjects were imaged with ¹⁸F-EF5) and (2) determine whether glucose metabolism (as assessed by ¹⁸F-FDG PET/CT) is affected by NFV, and whether this corresponds to a decrease in ¹⁸F-FMISO uptake. NFV responders have a better treatment outcome than NFV non-responders will be tested by comparing PFS between these groups. The definition of "NFV responder" requires greater knowledge about the distribution and variance of the baseline T:M ratio. For example, a decrease in T:M ratio to <1.25 or percent decrease from baseline of >50% may be reasonable definitions.

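### Change in hypoxia is named as an early predictor of outcome but reaches outcome only through a responder split with an open cut; add it as a continuous variable to the Cox models already planned

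*Combined protocol and SAP*

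**What the plan says.** Section 7 (Statistical Plan) gives the pre/post-nelfinavir measurements a predictive role: "These pre/post-NFV changes are evaluated as 'early change' predictors of treatment outcome". That sentence names no model.

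Cox regression is planned in two places, both worded around baseline values. Section 3.3: "That baseline hypoxia and glucose metabolism are predictive of treatment outcome will be tested by Cox regression analysis". Section 7: "Baseline hypoxia, and glucose uptake are predictive of treatment outcome will be tested by an exploratory analysis using Cox regression", followed by "Each variable will be tested in a univariate survival model to assess association with locoregional control", with a hazard ratio and 95% confidence interval for each. The comma in the Section 7 sentence leaves it slightly unclear whether the glucose variable is baseline, but on neither reading is change in hypoxia in a Cox model.

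The link from change in hypoxia to outcome is a two-group comparison. Section 3.2: "NFV responders have a better treatment outcome than NFV non-responders will be tested by comparing PFS between these groups". Section 7: "Exploratory analyses will also evaluate differences between Nelfinavir responders and nonresponders". The responder definition is left open because it "requires greater knowledge about the distribution and variance of the baseline TMR". Both sections give the same two examples: a post-nelfinavir tumour-to-muscle ratio (TMR) below 1.25, or a fall of more than 50% from baseline. Section 7 closes: "This exploratory analysis yields estimates of treatment outcomes within response groups".

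Pre/post hypoxia on its continuous scale is otherwise used only in the paired t-test and in a Pearson correlation with change in glucose uptake. Neither is an outcome analysis.

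**The concern.** The protocol's central hypothesis (end of Section 1.1) is that nelfinavir lowers tumour hypoxia and that this contributes to radiosensitisation and better outcome. Change in hypoxia is the variable that carries this hypothesis, yet it gets the coarser analysis while the baseline values get a hazard ratio and interval. No reason is given for the difference.

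The example cuts show what grouping does. A tumour going from TMR 1.30 to 1.24, a fall of 0.06/1.30 = 5%, is a responder on the first definition. A tumour going from 3.0 to 1.6, a fall of 1.4/3.0 = 47%, is a non-responder on both. Such groups say little about whether a larger fall goes with better control. With few events, a real association would be missed more often than necessary, and a null comparison could be misread as evidence against the mechanism.

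**Working it through.** **Inputs from Section 7.** 28 patients; 4 years of accrual plus 6 months of follow-up; 3-year locoregional control of 40% (null) and 70% (target); one-sided 5%, the level of both powered tests there.

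**Assumptions not in the documents.** HR per SD of change (1.25 to 2.5 shown); normally distributed change; exponential times; uniform accrual; no other censoring; both scans in all 28 patients; one-sided 5% for this analysis.

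**1. The plan's nearest figure.** No power is stated for relating change to outcome. The nearest is 82% for the paired t-test. Noncentrality 0.5 × √28 = 2.646 on 27 df at one-sided 5% gives 82.5%, so it reproduces. It concerns whether TMR falls, not whether the fall predicts outcome.

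**2. Expected locoregional events.** With rate λ, events = 28 × [1 − (e^(−0.5λ) − e^(−4.5λ))/(4λ)].
- 70% control: λ = −ln(0.70)/3 = 0.1189 per year; 28 × (1 − 0.750) = 7.0.
- 40% control: λ = −ln(0.40)/3 = 0.3054 per year; 28 × (1 − 0.4955) = 14.1.

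**3. Information kept by a cut.** For a normal predictor with a log-linear effect, a cut with share p in one group keeps φ(z_p)²/[p(1−p)].
- Median: 0.3989²/0.25 = 0.637, so about 36% is lost.
- 25/75: 0.3178²/0.1875 = 0.539, so about 46% is lost.

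The formula is symmetric in p. With few events, actual power is not, as step 5 shows.

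**4. Approximate power at 7 events, HR 1.5.**
- Continuous: Φ(√7 × ln 1.5 − 1.645) = Φ(1.073 − 1.645) = 28.4%.
- Median split: Φ(1.073 × √0.637 − 1.645) = Φ(−0.789) = 21.5%.
- Loss: 6.9 points.

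**5. Simulation.** 20,000 trials per row, hazard proportional to exp(βX) with larger X meaning a smaller fall, baseline rate solved for 70% or 40% marginal 3-year control, censoring uniform on 0.5 to 4.5 years. Cox score test on X against log-rank on each split; power in %, one-sided 5%.

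| 3-year control | HR per SD | Continuous | Median split | 25% non-responders | 25% responders |
|---|---|---|---|---|---|
| 70% (7 events) | 1.0 | 5.2 | 4.8 | 6.8 | 2.8 |
| | 1.25 | 14.2 | 11.3 | 14.1 | 5.9 |
| | 1.5 | 26.8 | 19.8 | 24.3 | 9.3 |
| | 2 | 52.1 | 36.7 | 43.2 | 17.6 |
| | 2.5 | 70.7 | 50.6 | 58.5 | 23.9 |
| 40% (14 events) | 1.0 | 5.6 | 5.3 | 7.0 | 4.0 |
| | 1.25 | 20.3 | 16.1 | 18.2 | 11.7 |
| | 1.5 | 42.1 | 30.7 | 32.9 | 21.5 |
| | 2 | 77.3 | 58.2 | 60.8 | 41.3 |
| | 2.5 | 92.3 | 75.8 | 79.1 | 56.7 |

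Allowing about one point for simulation error, the losses against the continuous test are:
- Median split: 2 to 4 points at HR 1.25; 7 to 12 at 1.5; 15 to 21 at 2 to 2.5.
- 25% non-responders: about 3 to 17 points at HR 1.5 to 2.5.
- 25% responders: about 18 to 47 points at HR 1.5 to 2.5.

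The HR 1.0 rows matter. The 25% non-responder split rejects somewhat too often and the 25% responder split too rarely, so part of those two contrasts is unequal test size. Continuous and median-split tests are close to nominal.

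**6. Two checks on generality.** At two-sided 5%, 7 events and HR 1.5, power is 17.3% continuous, 12.0% median split and 16.5% with 25% non-responders: losses of 5.3 and 0.8 points. If the true effect is a step exactly at a median cut, with HR 4 between groups and 7 events, the split has 52% power (one-sided 5%) and the continuous test 37%.

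**The case against.** **It is exploratory and no power is claimed.** True, and it limits the weight of the point. But the baseline Cox models are equally exploratory and still get a hazard ratio and interval, and Section 3.2 says the responder hypothesis will be tested. The label does not explain the difference. Nothing in the plan bars a continuous model as well; it simply plans none.

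**A responder group can ask its own question.** A TMR below 1.25 is a cut on the post-treatment level, close to the 1.3 that Section 3.3 uses to call a tumour hypoxic. It asks whether the tumour stopped being hypoxic, which a model of log(post/pre) does not capture. If that threshold is what matters, the split can win, as step 6 shows. This stands, and is a reason to keep the grouping as a supporting analysis.

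**The endpoint differs.** Section 3.2 compares progression-free survival, which counts more events than locoregional control. The 7 to 14 events do not describe that comparison.

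**The remedy stays weak and faces two tracers.** At about 7 events the continuous test itself has only 27% power at HR 1.5 and 52% at HR 2. The first 15 subjects were imaged with EF5 and later ones with FMISO, so pooling needs a common scale. Both points stand.

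**Stronger readings to avoid.** A reader might infer that any cut costs at least 7 points, that a median split is always the least harmful cut, or that every 25/75 split costs 20 points or more. The documents fix no effect size, test level or cut that would support these. Weak effects, a 25% non-responder group and a true threshold each contradict the first. The 25% non-responder split beats the median split at every HR above 1 in the table, though its size is slightly inflated. The very large losses arise only when the small group is the responders.

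**Conclusion.** The gap is real: the plan gives change in hypoxia a predictive role but provides no model of outcome on the continuous change, only a grouping whose definition is undecided. Under a roughly log-linear effect, a median split gives up about 36% of the information. The power cost ranges from a few points for a weak effect to about 20 for a strong one; it is less with few non-responders and much more with few responders. These figures rest on an assumed HR per SD, locoregional events, one-sided 5% and complete paired scans. Section 3.1 lets scans be excused, so the usable number may be lower. They do not show that the responder analysis is invalid, or that a continuous analysis would be well powered. It is an improvement worth making because the data are already collected.

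**What to change.** In Section 7, extend the planned univariate Cox models with wording such as:

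> Change in hypoxia, log(post-NFV TMR / pre-NFV TMR), will be entered as a continuous variable in a Cox model for locoregional control, standardised within tracer or stratified by tracer (EF5 or FMISO), reporting the hazard ratio with 95% CI. Change in FDG uptake will be analysed in the same way, without the hypoxia-tracer adjustment.

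Choose between standardising and stratifying before outcomes are examined. Make this model the main exploratory test of the early-change hypothesis, keep the responder grouping as a supportive, descriptive analysis, and align the Section 3.2 sentence, including its endpoint.

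**Cost.** A few sentences and two further Cox models; no new patients, scans or visits. The model assumes a roughly log-linear effect, which a residual plot can check, and a comparable scale across tracers after adjustment. Power stays modest with about 7 events, so the interval should be reported and a null result not read as evidence against the mechanism.
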